Prepare according to (Note) 1 to 7 in Attachment form 2 of PFSB/ELD Notification No. 1027004 of Director of Pharmaceutical Evaluation Division dated October 27, 2005. Attach a list of adverse drug reactions/infections by patient unit to the far right of this table.

Prepare a list of onset of adverse drug reactions according to administration category (initial administration, re-administration 1, re-administration 2, re-administration 3 onward) and treatment period (≤ 56 days, ≥ 57 days, unknown) in the same manner shown in Attachment form 2.

Accumulation and total section in (Note) 2

- The same site participating in Ph 2 and Ph 3 is counted once concerning the number of surveyed sites up to approval.
- A report submitted by the same site for the first and second reporting is counted once concerning

cumulative total section for the number of surveyed sites.

- A report submitted from the same site prior to approval and during a special drug use survey is counted once concerning a total section of a number of surveyed sites.

Number of occurrences of same adverse drug reactions/infections encountered in the same patient in (Note) 3

- In tabulation of SOC, several occurrences of the same SOC in a given patient is counted once.
- In tabulation of PT, several occurrences of the same PT in a given patient is counted once.

Infections in (Note) 7

- No infection was collected or reported by the time of obtaining approval.

Percentage (%) of number of onset (occurrence) of adverse drug reactions by types in (Note) 7

- Calculate percentage (%) for the number of patients by types (occurrences) to the second decimal place (round up to the second decimal place). The same is applied hereinafter unless otherwise stated.

3) List of occurrences of serious adverse events (Attachment form 10 of the notification of Director of Ministry of Health, Labour and Welfare)

<Analysis population>

Patients included in safety evaluation.

<Preparation method>

Prepare according to (Notes) 1 to 8 in Attachment form 10 of PFSB/ELD Notification No. 1027004 of Director of Pharmaceutical Evaluation Division dated October 27,2005. Present serious adverse events by patient unit at the far right of this table.Cumulative total and total section in (Note) 3

- The same site that participates in Ph 2 and Ph 3 studies is counted once concerning the number of surveyed sites up to approval.

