- A report submitted by the same site for the first and second reporting is counted once concerning cumulative total section for the number of surveyed sites.
- A report submitted from the same site prior to approval and during a special drug use survey is counted once concerning a total section of a number of surveyed sites.

Number of adverse events encountered in the same patient in (Note) 4

- In tabulation of SOC, several occurrences of the same SOC in a given patient is counted once.
- In tabulation of PT, several occurrences of the same PT in a given patient is counted once.

4) List of seriousness, date of onset, outcome of adverse drug reactions

<Analysis population>

Patients included in safety evaluation.

<Preparation method>

Tabulate seriousness, date of onset, and outcome of adverse drug reactions by types according to the category in the following table (2). Adverse drug reactions will be handled according to the “2) List of onset of adverse drug reactions/infections (Attachment form 2 of the notification from director of MHLW)”. However, in case of several occurrences of adverse drug reactions classified into the same PT in a given patient, select the most serious for seriousness, initial onset for the date of onset of adverse drug reactions, and the severest outcome.

Seriousness: serious>non-serious

Time of onset: event with earlier onset

Outcome: death> recovered with sequela> not recovered> improved> recovered >unknown

Prepare a list of adverse drug reactions according to administration category (initial administration, re-administration 1, re-administration 2, re-administration 3 onward) and treatment period (≤ 56 days, ≥ 57 days) in the same manner

Table (2) Category of seriousness, date of onset, and outcome

Item	Category
Seriousness	1) serious, 2) non-serious, 3) unknown
Timing of onset ^{*1}	1) Day 1 - 7, 2) Day 8 - 14, 3) Day 15 - 21, 4) Day 22 - 28, 5) Day 29 - 56, 6) Day 57 - 84, 7) Day 85 - 180, 8) Day 181 - 210, 9) Day 211 - 360, 10) Day 361 onward, 11) unknown
Outcome	1) recovered, 2) improved, 3) not recovered, 4) recovered with sequela, 5) death, 6) unknown

*1: number of days counted from the “date of starting administration” as “Day 1” until “date of onset of adverse drug reactions”.

5) Onset of adverse drug reactions by factors

<Analysis population>

Patients included in safety evaluation.

<Preparation method>

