All patients in spontaneous reporting, literature, drug use surveillance, special drug use survey, clinical trials, post-marketing clinical trials, and a clinical trial conducted by other pharmaceutical company.

<Preparation method>

Concerning serious adverse drug reactions, number of patients will be calculated for each type of adverse drug reactions (according to SOC and PT) by the timing of onset and outcome category shown in Table (2). In case of several occurrences of the same adverse event/adverse drug reaction (LLT) in a given patient, they will be tabulated as one according to the priority order in 4). Events with the same PT but different LLT will be tabulated as separate events.

11) Profile table of adverse drug reactions not foreseeable from “Precautions”

<Analysis population>

All patients in spontaneous reporting, literature, drug use surveillance, special drug use survey, clinical trials, post-marketing clinical trials, and a clinical trial conducted by other pharmaceutical company.

<Preparation method>

Concerning the adverse drug reactions not foreseeable from “Precautions”, number of patients for each types of adverse drug reactions (SOC, PT) will be calculated based on the categories of seriousness, timing of onset, and outcome shown in Table (2). In case of several occurrences of the same adverse event/adverse drug reaction (LLT) in a given patient, they will be tabulated as one according to the priority order in 4). Events with the same PT but different LLT will be tabulated as separate events.

(5) Efficacy analysis

1) Changes in excess serum ALP

<Analysis population>

Patients included in efficacy evaluation. However, patients without baseline data or post-administration data will be excluded.

<Preparation method>

For excess serum ALP, measured value at each time point and percent change from baseline will be calculated and summary statistics and two-sided 95% confidence interval will be shown. A paired t-test will be conducted for percent change and p-value of test results will be shown. Details of handling of data at each time point will be shown in “(8) Other arrangements 5) Data of evaluation time point”.

A graph showing changes in mean \pm standard deviation will be prepared for the measured values at each time point and percent change.

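### The profile tables in SAP 5.(4)10) and 11) are defined as numbers of patients per PT, but their counting rule can count one patient twice in a PT row

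*SAP*

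**What the plan says.** The current SAP (version 4.1) specifies two profile tables for re-examination: 5.(4)10) for serious adverse drug reactions and 5.(4)11) for reactions that the Precautions do not foresee.

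- **Unit.** Table 10) says "number of patients will be calculated for each type of adverse drug reactions (according to SOC and PT"), split by onset time and outcome. Table 11) says "number of patients for each types of adverse drug reactions (SOC, PT) will be calculated", split by seriousness, onset time and outcome.
- **Counting rule.** Both say "In case of several occurrences of the same adverse event/adverse drug reaction (LLT) in a given patient, they will be tabulated as one", using the priority order of table 4). Both then add "Events with the same PT but different LLT will be tabulated as separate events".

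Other safety outputs merge repeats at a higher level. List 2), for adverse drug reactions, and list 3), for serious adverse events, both state "In tabulation of PT, several occurrences of the same PT in a given patient is counted once", with a matching once-per-patient rule for SOC. Table 4) applies its priority order "in case of several occurrences of adverse drug reactions classified into the same PT in a given patient".

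Section 3 sets a default unit: a re-administered person counts once for each CRF unless an output states that it is tabulated by patient unit. Neither table 4) nor tables 10) and 11) state this.

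**The concern.** In MedDRA, one PT can hold several LLTs. Merging within LLT leaves one record per patient and LLT, not one per patient and PT. The text then enters those records in a cell that it calls a number of patients. For a patient with two LLTs under one PT, the label and the rule give different answers.

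These tables summarise serious and unforeseen reactions for the re-examination documents. A reader who sees two patients in a row, one recovered and one not recovered, has no means of telling that they are the same person. Two programmers could also read the text differently, one filling the cells with distinct patients and the other with distinct LLT records.

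The SAP keeps the two quantities apart elsewhere: 5.(4)5) lists patients with reactions and occurrences of reactions as separate items.

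**Working it through.** The documents give no figure to reproduce, so the check compares the rules and then applies them to small hypothetical rows.

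**The outputs side by side**

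| | Table 4) | Tables 10) and 11) |
|---|---|---|
| Cases | "Patients included in safety evaluation", this survey only | Spontaneous reports, literature, surveys, clinical trials, another company's trial |
| Reactions | All adverse drug reactions | Serious only in 10), unforeseen only in 11) |
| Re-examination lock point, section 4.(1) | 12th, March 31, 2018 | 13th, July 15, 2018 |
| Repeats within a patient merged by | PT | LLT |
| SOC rule | Follows list 2): once per patient | None stated |

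**Formula.** For one PT row, let k be the number of different LLTs that a patient has under that PT.

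- LLT rule, as in 10) and 11): row total = sum of k over patients.
- Patient count: number of patients with k of at least 1.
- Excess: sum of (k − 1).

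**Row A.** Two patients have a serious reaction in the PT, and one of them has two LLTs. LLT rule: 2 + 1 = 3. Patients: 2. Excess: 1.

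**Row B.** The same two patients, but the repeat event has the same LLT. LLT rule: 1 + 1 = 2. Patients: 2. Excess: 0. The rules differ only when some patient has k of at least 2.

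**Row C.** Row B plus one spontaneous report in a third patient. Table 4) shows 2, because it covers survey patients only. Table 10) shows 3 under the LLT rule and also 3 under a PT rule. The gap comes from the source of cases, not from the counting rule.

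**Cells within Row A.** Suppose the patient's first LLT begins in Days 8–14 and ends as recovered, and the second begins in Days 29–56 and ends as not recovered (categories of Table (2)). Under the LLT rule this one patient fills two onset cells and two outcome cells. One record per PT under the order in 4) would give Days 8–14 (earlier onset) and not recovered (worse outcome).

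**SOC row.** Lists 2) and 3) collapse explicitly at SOC. Tables 10) and 11) do not, so summing PT rows would carry the excess of 1 into the SOC row. The text does not say whether that is intended.

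**Person or CRF.** Under section 3, a re-administered person with the same PT in two CRFs counts as 2 even with PT-level merging, in table 4) as well. This is a separate route to multiple counting, and a PT-level rule would not remove it.

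**The case against.** Four objections carry weight.

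1. **The tables were never meant to agree with table 4).** A reader might infer that the LLT rule will stop the survey cases from reconciling with that table. The documents do not support this. Sources, event scope and lock point differ by design, no reconciliation is promised, and no breakdown of 10) or 11) by source is specified. Row C shows a gap under either rule. All that stands is that, for the same patients and the same events, the two rules can give different PT counts.
2. **The size is unknown.** A reader might also infer that the tables are inflated. Nothing in the documents says how often a patient has two LLTs under one PT. Where none does, the label and the rule coincide, as in Row B.
3. **The LLT level may be deliberate.** A profile by onset time and outcome loses detail if distinct events are merged, and the order in 4) works at any level of the dictionary. This stands, and it is why the fix keeps the LLT tabulation. It does not make those records patients.
4. **Patient-level PT counts exist elsewhere.** For survey patients, lists 2) and 3) and table 4) supply them, and neither 10) nor 11) specifies a percentage or test. This limits the damage. It does not cover the cases from other sources, and no other section corrects the label.

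It can also be said that the instruction on different LLTs is explicit, so only the label is loose. That is largely right, but the label decides how the numbers are read.

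**Conclusion.** The point holds as an error of unit. Tables 10) and 11) promise patients by SOC and PT and prescribe a count of patient-by-LLT events. A patient with two LLTs under one PT is counted twice in that PT row, possibly twice in the SOC row, and can appear in two timing or outcome cells.

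The size is one extra count for each additional LLT that a patient has under a PT. Without a frequency in the documents, the effect on the final tables runs from zero upward. The rows above are illustrations, not estimates. The conclusion assumes that the rule is programmed as written and that the cells keep their patient label.

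This is a minor point: it concerns how two descriptive tables are read and affects no test in the plan.

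**What to change.** In 5.(4)10) and 11):

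- Keep the LLT-level tabulation, but label those cells as number of events.
- Add a number of patients, counted once per PT and once per SOC, with the order in 4) deciding which onset time, outcome and seriousness represent the patient.
- State in the table header whether the patient unit is the CRF or the person. Section 3 leaves it at the CRF by default, and it is worded for survey CRFs while these tables also take cases from other sources.

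The cost is a short SAP wording change, one extra column and a second de-duplication key. Event detail is kept. The change will not make the totals equal to table 4), and a table note could say so.

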X-ray is conducted at Week 4, or when simple X-ray and bone scintigraphy are conducted at Week 8, during observation period, and Week 48 (completion of observation period), date of examination and assessment findings (improvement, unchanged, aggravation of bone morphology, trabecular bone structure and other abnormal findings by simple X-ray, compared with baseline) should be recorded.

When CT and MRI is conducted at baseline, record the findings.

(6) Adverse events

Record the name of an adverse event that developed after the baseline and before completion of observation period, date of onset, seriousness, action taken, outcome, and causal relationship with this drug to be evaluated. Follow up adverse events until recovery as best as possible.

(7) Laboratory test

Conduct general hematology, blood chemistry, and urinalysis at baseline and during observation period and record the test item assessed as abnormal variation compared with baseline in the adverse events section of CRF. Record the laboratory test data of the item assessed as abnormal variation in “Variation of laboratory test data assessed as abnormal variation” section.

8. Items and method of analysis

(1) Analysis population

Conduct analysis for all patients administered this drug.

Conduct analysis of the patients above according to the baseline demographics and pathology.

(2) Demographic factors

Tabulate patients by sex, age, weight, morbid period, prior therapy, concomitant drugs.

(3) Efficacy endpoint

1) Serum ALP, bone metabolism markers

i) Serum ALP

Calculate summary statistics (mean, standard deviation, minimum, maximum) and 95% confidence interval for the excess serum ALP measured at baseline, Week 4, Week 8, during observation period, and Week 48. Conduct one-sample t-test for percent change in excess serum ALP. Show time-course of change at baseline, Week 4, Week 8, during observation period, and Week 48.

*Excess serum ALP: actual value of serum ALP — (maximum of reference value + minimum of reference value)/2

ii) Bone metabolism marker

Calculate the mean and standard deviation for the values measured before and after administration. Conduct one-sample t-test for percent change.

2) Tabulation of pain associated with osseous Paget's disease

Show distribution of pain severity at each time point of baseline, Week 4, Week 8, during observation period, and Week 48.

3) Treatment compliance

Conduct frequency tabulation for treatment compliance during treatment period.

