To observe the efficacy and safety of BENET Tablets 17.5 mg/Actonel Tablet 17.5 mg in patients with osseous Paget's disease up to Week 48 as an all-case surveillance based on the approval conditions.

2. Patients to be included in analyses

(1) Breakdown of patients to be included in analyses

“Patients included in safety evaluation” and “patients included in efficacy evaluation”.

(2) Patients included in safety evaluation

Of the patients from whom a case report form (CRF) is collected, those who satisfy either of the following conditions are excluded from safety evaluation and others are included in safety evaluation.

- i) A patient not administered this drug
- ii) A patient in whom onset of adverse event is unknown
- iii) Of the patients with duplicated enrollment, those who were enrolled later.
- iv) A patient for whom administration was started outside the enrollment period*

* The date of starting administration falls after the enrollment period of January 31, 2016 (on and after February 1, 2016).

(3) Patients included in efficacy evaluation

Of the patients included in safety evaluation, those who satisfy the following conditions are excluded from efficacy evaluation and others are included in efficacy evaluation.

- i) patients from whom the information on efficacy before and after administration was not obtained.

3. Handling of patients

Unless otherwise specified, a patient recorded in a different CRF as a re-administered patient will be tabulated as one patient based on each CRF even if he/she is the same person. When tabulating the same patient as one patient, it should be clarified in “creation method” that tabulation is conducted for “each patient unit”.

4. Data Lock Point

(1) Data Lock Point

Date of starting survey: August 1, 2008

Data Lock Points (DLP) are shown below.

1st: September 30, 2008

2nd: March 31, 2009

3rd: September 30, 2009

4th: March 31, 2010

5th: March 31, 2011

6th: March 31, 2012

7th: March 31, 2013

8th: March 31, 2014

9th: March 31, 2015

10th: March 31, 2016

11th: March 31, 2017

12th: March 31, 2018, re-examination

13th: July 15, 2018, re-examination “(4) Safety analysis 10) Profile Table of serious adverse drug reactions,

11) Profile Table of adverse drug reactions not foreseeable from ‘Precautions’”

5. Tabulation and analysis at each DLP

(1) Patient composition diagram

<Analysis population>

Enrolled patients.

<Preparation method>

- 1) number of study sites
- 2) number of enrolled patients

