Of the patients whose upper limit of the site reference value* is available among those who receive initial administration, percentage of patients will be calculated in whom post-dose serum ALP is lowered by 10% compared with baseline and <2-fold of the upper limit of the site reference value at each time point.

* In case baseline site reference value is available but post-dose site reference value is missing, complement data with baseline site reference value.

5) Changes in serum ALP (subgroup analysis)

<Analysis population>

i) Patients included in efficacy evaluation. However, a patient without baseline or post-administration data will be excluded.

ii) Patients who received initial administration. However, it is not applicable to administration categories 1 and 2 because they are comparison with the initial administration.

<Preparation method>

Serum ALP will be stratified by the items shown in Table (4), measured value at each time point and percent change from baseline will be calculated and summary statistics and two-sided 95% confidence interval will be shown. Paired t-test will be conducted for percent change and p-value will be shown for the test result.

6) Changes in serum ALP (subgroup analysis 2)

<Analysis population>

Patients included in efficacy evaluation and who receive re-administration. However, a patient without baseline or post-administration data will be excluded.

<Preparation method>

Changes in serum ALP and the percent change at initial administration, re-administration 1 and 2 will be shown for each patient.

7) Changes in bone metabolism markers

<Analysis population>

Patients included in efficacy evaluation. However, a patient without baseline or post-administration data will be excluded.

<Preparation method>

Measured value at each time point and percent change from baseline will be calculated for each item of bone metabolism markers.

Summary statistics will be calculated, paired t-test will be conducted for percent change, and p-value will be shown for the test result. A graph showing changes over time in mean \pm standard deviation will be prepared for the measured values. Details of handling of data at each time point will be shown in “(8) Other arrangements 5) Data of evaluation time point”.

8) Evaluation of pain associated with osseous Paget's disease

<Analysis population>

Patients included in efficacy evaluation. However, a patient without baseline or post-administration data will be excluded.

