<Preparation method>

A cross-tabulation table will be prepared for evaluation of pain associated with osseous Paget's disease before and after administration at each evaluation time point. Details of handling of data at each time point will be shown in “(8) Other arrangements 5) Data of evaluation time point”.

Bowker's test of symmetry will be conducted for changes in severity of pain before and after administration.

Severity of pain will be scored as shown below prior to analysis.

no pain \rightarrow 0, not disturbing \rightarrow 1, tolerable \rightarrow 2, unbearable \rightarrow 3

Number of patients with pain associated with osseous Paget's disease by the site of pain and percentage will be calculated at each time point.

9) Imaging findings

<Analysis population>

Patients included in efficacy evaluation. However, a patient without baseline or post-administration data will be excluded.

<Preparation method>

A cross-tabulation table before and after administration will be prepared for bone morphology, trabecular bone structure, and other abnormal findings by imaging findings (simple X-ray) at each time point. Details of handling of data at each time point will be shown in “(8) Other arrangements 5) Data of evaluation time point”.

In case only “no pain” or “presence of pain” is recorded as evaluation finding after administration without recording of “improved”, “no change”, or “worsened”, evaluation will be made as follows.

Baseline	Post-dose	Evaluation
No pain	No pain	No change
No pain	Presence of pain	Worsened
Presence of pain	No pain	Improved

Baseline	Post-dose	Evaluation
Presence of pain	Presence of pain	Not evaluable

(6) Analysis of patients excluded from safety evaluation

1) List of onset of adverse drug reactions

<Analysis population>

Patients excluded from safety evaluation.

<Preparation method>

Analysis shown in “2) List of onset of adverse drug reactions/infections (Attachment form 2 of notification from director of MHLW)” in “(4) Safety analysis” will be conducted. However, total results from the first reporting up to this report will be combined instead of tabulation for each timing.

2) List of seriousness, date of onset, outcome of adverse drug reactions

<Analysis population>

Patients excluded from safety evaluation.

<Preparation method>

Analysis shown in “4) List of seriousness, date of onset, outcome of adverse drug reactions” in “(4) Safety analysis” will be conducted.

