In case several efficacy data exist for the same time point, proceed as shown below.

- 1) Select the data on the day closest to the standard date.
- 2) In case there are more than one data with the same number of days before or after the standard date, select the data after the standard date. However, select the data before the date of administration of this drug when time point is baseline.

6) Excess serum ALP

Excess serum ALP will be calculated as follows.

excess serum ALP = measured value of serum ALP - (maximum reference value + minimum reference

value)/2

However, denominator may become “0” when calculating percent change 4). When excess serum ALP becomes “0”, calculate the value as “0.01”.

7) Handling of patients who receive re-administration

Initial administration and re-administration will be judged based on “administration category” of CRF.

Whether or not the same patient has received re-administration will be judged based on the information on re-administration separately managed. When a patient has received several re-administrations, arrange them in a temporally order and number them re-administration 1 and 2 starting with the earliest date.

A previous case will be completed when re-administration is started. Accordingly, the efficacy data after the start of re-administration recorded in the prior CRF will not be used.

8) Calculation method for intervals of re-administration

Calculate number of days from the date of completion of previous administration (date of completion of administration for the initial administration in case of re-administration 1) up to the date of starting administration.

interval of re-administration = date of administration of this drug - date of completion of previous administration of this drug

9) Tests

Tests will be conducted by excluding “unknown”. p-value will be calculated up to the 4th decimal place (round up to the 4th decimal place).

10) Output of category “unknown”

In case category is “unknown” and target number of patients is 0, category “unknown” is not outputted.

**Benet 17.5 mg Tablets Special Drug Use Surveillance in Patients With
Osseous Paget's Disease (All-case Surveillance)**
**Actonel 17.5 mg Tablets Special Drug Use Surveillance in Patients With
Osseous Paget's Disease (All-case Surveillance)**
- 48-week surveillances-

Statistical Analysis Plan Version 4.0

Takeda Pharmaceutical Co., Ltd.

PPD

Change history

Version No.	Date of preparation/revision	Site/reason for change

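### Pain is scored 0 to 3, but the only test of change, Bowker's test of symmetry, uses neither the order of the scores nor a common direction

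*SAP*

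**What the plan says.** The current SAP (Ver. 4.1), section 5.(5)8), handles pain as follows:

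- A before/after table at each time point: "A cross-tabulation table will be prepared for evaluation of pain associated with osseous" Paget's disease.
- Bowker's "test of symmetry will be conducted for changes in severity of pain before and after administration".
- Scores from 0 (no pain) to 3 (unbearable): "Severity of pain will be scored as shown below prior to analysis".
- Counts and percentages by site of pain.

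No other test and no effect estimate is given for pain. The general rule in SAP 5.(8)9) drops unknown values and fixes the digits ("p-value will be calculated up to the 4th decimal place"). It gives no df rule for empty cell pairs and no exact method.

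The pain population is: "Patients included in efficacy evaluation. However, a patient without baseline or post-administration data will be excluded". Under SAP 3, a re-administered patient with a separate CRF "will be tabulated as one patient based on each CRF even if he/she is the same person" unless otherwise specified, and the pain section does not specify otherwise. The ALP subgroup analyses in SAP 5.(5)2) and 5.(5)5) add a restriction ("Patients who received initial administration"), waived only for the administration-category strata.

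Protocol 8.(3)2) plans no test for pain: "Show distribution of pain severity at each time point of baseline, Week 4, Week 8, during observation period, and Week 48". Protocol 7.(5) lists pain first among the secondary endpoints.

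**The concern.** The natural question for an ordered 0 to 3 score is whether patients moved towards less pain. Bowker's test asks whether any of the six pairs of opposite cells in the 4×4 table is unbalanced. Relabelling the pain levels in any order leaves its statistic unchanged, so the scores assigned beforehand play no part in it.

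Two misreadings follow. A non-significant result could be taken as no change when nearly every changer improved. A significant result could be taken as improvement when improvement and worsening cancel out. The p-value goes into the re-examination documents, where a reader would expect it to speak for or against relief of pain.

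A second problem affects any paired test here: if one person contributes several CRFs, the pairs need not be independent.

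**Working it through.** **Inputs.** Four levels give 6 cell pairs (SAP 5.(5)8)). No alpha is stated for pain. I assume two-sided 0.05, the only threshold in the SAP, used in 5.(4)6) for adverse drug reaction factors. The number of patients is not fixed (Protocol 2), so the number of changers is varied. The documents give no power or effect figure for pain to reproduce.

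**1. Upper bound.** Bowker's statistic is the sum over pairs of (a−b)²/(a+b), where a and b are the counts in opposite cells. Each term is at most a+b, so the statistic is at most the number of changers D, and it equals D when all improve. The exact signed-rank p-value is then 2×0.5^D: 0.0625 at D=5 and 0.031 at D=6, so 6 are needed.

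| df used | chi-square 95% point | all-improving changers needed, Bowker | needed, exact signed-rank |
|---|---|---|---|
| 1 | 3.841 | 4 | 6 |
| 2 | 5.991 | 6 | 6 |
| 3 | 7.815 | 8 | 6 |
| 4 | 9.488 | 10 | 6 |
| 5 | 11.070 | 12 | 6 |
| 6 | 12.592 | 13 | 6 |

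If df is always 6, D=12 gives p=0.062 and D=13 gives 0.043; signed-rank at D=12 gives 0.0005. If df is the number of non-empty pairs, the row depends on how the changers spread. Bowker's test then needs fewer with one pair, the same with two, and more with three or more.

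**2. Small counts in one pair.** With 4 changers, only a 4–0 split exceeds 3.84. The chi-square p-value is 0.0455, but the exact p-value is 2/16 = 0.125. With 8 changers, splits of 7–1 or 8–0 reject, with null probability 2×(8+1)/256 = 7.0%. Other counts fall below 5%, for example 3.1% at 6.

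**3. Zero net change.** Seven patients go from 1 to 0 and seven from 2 to 3. The statistic is 7²/7 + 7²/7 = 14, so p=0.030 on 6 df or 0.0009 on 2 df. Signed-rank gives 1.0. The unstated df rule alone changes the p-value more than thirty-fold.

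**4. Power, under an assumed model.** A latent bivariate normal variable was cut at 35/65/90%, with correlation 0.5 and 0.8, a shift of 0.25 and 0.5 SD, one record per person, and 3,000 runs per setting. Ranges run across these settings.

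| n | mean changers | Bowker, 6 df | Bowker, non-empty df | exact signed-rank |
|---|---|---|---|---|
| 12 | 5–7 | 0% | 1–6% | 5–22% |
| 30 | 13–17 | 1–18% | 5–44% | 18–81% |
| 50 | 22–29 | 6–65% | 9–80% | 30–97% |
| 80 | 35–46 | 15–95% | 17–98% | 45–100% |
| 120 | 52–69 | 31–100% | 32–100% | 63–100% |

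With no shift, signed-rank rejects 1.1–5.0%, Bowker 0.4–3.7% (non-empty df) or 0–3.3% (6 df).

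**5. Repeated persons.** Three people who each improve in two CRFs give signed-rank p = 2×0.5⁶ = 0.031 counted by CRF, but 2×0.5³ = 0.25 counted by person. Null rejection was simulated with 30 or 50 persons, 30–50% of them with one extra CRF or 50% with two, baseline–post correlation 0.5, and a person-specific share of the remaining variance of 0.5 or 0.8:

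| Test | each CRF as a patient | initial administration only |
|---|---|---|
| Signed-rank | 6.5–17.0% | 3.6–5.0% |
| Bowker, non-empty df | 3.1–17.4% | 1.4–3.0% |
| Bowker, 6 df | 1.5–15.8% | 0.4–1.8% |

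**The case against.** Symmetry is a legitimate null hypothesis for change, and the SAP does not say that it tests improvement. In the zero-net example Bowker's test detects a real redistribution: seven patients reached unbearable pain, and signed-rank reports nothing. It can also be the more sensitive test. Eight patients going from 3 to 2, with balanced 5/5 changes in two other pairs, give p=0.046 (3 df) against 0.18. This stands, and it is a reason to keep Bowker's test alongside a directional one.

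The cross-tabulation lets a reader count improvers, and no alpha or success rule exists for pain. Both points are true and limit the severity.

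The power model assumes a location shift, which favours signed-rank. At n=12 neither test helps, and with the larger shift at n=80 to 120 both approach 100%. The one-pair anti-conservatism is also not general: from 6 to 30 changers the exact null rejection moves between 1.6% and 7.8%. These limits stand.

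Counting each CRF as a patient is an SAP-wide rule that also reaches the main ALP tests in 5.(5)1) and 5.(5)4). That is correct, but it does not make the pain pairs independent.

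Finally, Bowker's test has been specified since Ver. 2.0 in 2010. A new test now would follow pain analyses scheduled at earlier data lock points, so it must be labelled as late.

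**Conclusion.** The point holds. The single test named for pain ignores the order of the scores it is given. It can miss a uniform improvement (up to 12 changers on 6 df), and it can be significant with no net change. Its p-value also depends on a df rule that the SAP does not state, and repeat CRFs can enter as independent patients.

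The practical loss is material only if changers are few or the shift is small. The documents neither show nor exclude this: 12 patients is the pre-approval figure, while this survey enrols all treated patients over 7 years 6 months. Sample size, shifts, level frequencies, re-administration rates and the 0.05 level are assumptions. The primary ALP analysis is unaffected. The change should be made, but no formal decision depends on it.

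**What to change.** In SAP 5.(5)8):

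- Add an exact Wilcoxon signed-rank test (or an exact score-based marginal homogeneity test) on post-minus-baseline scores at each time point, as the test of directional change.
- Use one record per person, from the initial administration. Show re-administration CRFs descriptively in the cross-tabulation.
- Report the numbers improved, unchanged and worsened.
- Keep Bowker's test as the planned result and state its df rule for empty cell pairs.

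The cost is a few sentences and a few lines of code, with no new data. The new test treats score steps as comparable, can miss a change confined to one cell pair, and leaves re-administration CRFs out. It would also use a different population from the main ALP tests, which the text should say. Ver. 4.1 is dated March 30, 2018, one day before the re-examination lock, so the change history should record the test as a late addition.
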